**Figure 1 Study Schema: Randomized Treatment Phase (Treatment Period and Safety Follow-up Period)**

[figure not shown]

CD=Crohn's disease; OLE = open-label extension; Q4W = every 4 weeks; Q8W = every 8 weeks; UC=ulcerative colitis.

[figure not shown]
Notes: Etrolizumab dose: 1.5 mg/kg Q4W or 3 mg/kg Q8W SC injection of 0.01 mL per kg of patient weight.

Rescue therapy prescribed based on the discretion of the investigator and disease flare, can include methotrexate, corticosteroids, immunomodulators, and excludes anti-TNFs, vedolizumab, and other biologic agents (see Section 4.4.2.2). Based on the patients disease status and physicians care practices the patient can be withdrawn from the study at any time to receive excluded therapy.

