### **3. STUDY DESIGN**

#### **3.1 DESCRIPTION OF THE STUDY**

This pediatric PK/PD study consists of multiple phases. The randomized treatment phase is an open-label, randomized phase in which etrolizumab is administered to patients on the basis of body weight (mg/kg); randomization will be stratified by weight (<40 kg, ≥40 kg). Patients will be randomized in a 1:1 ratio to receive either high-frequency etrolizumab once every 4 weeks (Q4W) or low-frequency etrolizumab once every 8 weeks (Q8W). The high-frequency dose of 1.5 mg/kg etrolizumab will be administered Q4W (Weeks 0, 4, 8, and 12). The low-frequency dose of 3.0 mg/kg etrolizumab will be administered Q8W (Weeks 0 and 8).

After the 24-week randomized treatment phase (which includes a 16-week treatment period and an 8-week safety follow-up period), patients will then have the option to participate in the 312-week OLE phase (treatment with etrolizumab 1.5 mg/kg will be administered Q4W). All patients who participate in the 24-week randomized treatment phase and the 312-week OLE phase *will enter the 12-week safety follow-up period (see Appendix 1d; no etrolizumab treatment) and will complete the safety surveillance PML-monitoring phase (see Appendix 1e; no etrolizumab treatment for a total of 104 weeks)*. All patients who choose not to enter the OLE phase after the 24-week randomized treatment phase will enter the 104-week PML monitoring phase.

Patients can enter the OLE phase after completion of the 24-week randomized treatment phase. If the last visit of the randomized treatment phase and Day 1 of the OLE phase occur on the same day, the assessments from the randomized treatment phase should be completed. The assessments from the randomized treatment phase can apply to the OLE assessments (i.e., the same assessments should not be repeated for the OLE).

The 104-week PML monitoring phase will consist of telephone calls approximately every 6 months (see [Appendix 7](#)) with administration of the PML Subjective Checklist. If there are any signs or symptoms suggestive of PML identified on this subjective checklist during the telephone call, the patient will be asked to come into the clinic for a neurologic examination. The PML Algorithm (see [Appendix 8](#)) will be followed for any suspected

case of PML, and any confirmed case of PML will be reported as a serious adverse event (see Section 5.4.2).

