## **4.3 STUDY TREATMENT AND OTHER TREATMENTS RELEVANT TO THE STUDY DESIGN**

The investigational medicinal product (IMP) for this study is etrolizumab. All patients will receive etrolizumab one subcutaneous injection of 0.01 mL per kg of patient weight (1.5 mg/kg) Q4W or injection of 0.02 mL per kg of patient weight (3 mg/kg) Q8W.

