### **4.3.1 Study Treatment Formulation, Packaging, and Handling**

#### **4.3.1.1 Etrolizumab**

F. Hoffmann-La Roche Ltd manufactures etrolizumab drug product. Etrolizumab drug product is a colorless to slightly yellow solution. The drug product is a sterile and preservative-free liquid intended for SC administration.

The drug product contains 150 mg/mL of etrolizumab in 200 mM L-arginine succinate, 20 mM L-histidine, and 0.04% (w/v) polysorbate 20, pH 5.8. Etrolizumab drug product will be provided in single-use, 3-cc glass vials that are stoppered with 13-mm fluororesin laminated stoppers and capped with aluminum seals with flip-off plastic caps.

For further details, see the etrolizumab (PRO145223, RO5490261) Investigator's Brochure.

Upon arrival of investigational products at the site, the pharmacist or designee should check them for damage and verify proper identity, quantity, integrity of seals, and temperature conditions, and report any deviations or product complaints to the monitor upon discovery.

The study drug must be stored according to the details on the product label. The drug label indicates the storage temperature.

Under no circumstances is the investigator to allow study medication to be used other than as directed by the protocol.

Details about the packaging and labeling of the study drug will be provided in the protocol-supporting documents that include but are not limited to the study manual and laboratory manual.

For further details, see the current Investigator's Brochure.

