#### **4.3.2 Study Treatment Dosage, Administration, and Compliance**

##### **4.3.2.1 Etrolizumab**

The treatment regimens are summarized in Section [3.1](#).

Etrolizumab will be administered at the site during the randomized treatment phase. During the OLE phase, etrolizumab may be administered at the site.

Patients will receive treatment with etrolizumab 1.5 mg per kg patient weight SC Q4W weeks or 3 mg per kg patient weight SC Q8W. Injections will be administered to the abdomen. If the abdomen is not available for injection, the patient may receive a SC dose in the thigh. Each patient will receive one SC injection of 0.01 mL per kg patient weight or injection of 0.02 mL per kg of patient weight at each treatment visit based on the treatment regimen (the low or high frequency arm).

Etrolizumab vials are stable at 2°C–8°C (36°F–46°F). Etrolizumab vials should not be frozen or shaken and should be protected from direct sunlight.

Any overdose or incorrect administration of etrolizumab should be noted on the Study Drug Administration electronic Case Report Form (eCRF). Adverse events associated with an overdose or incorrect administration of any of the study treatments should be recorded on the Adverse Event eCRF.

Guidelines for etrolizumab treatment interruption or discontinuation for patients who experience adverse events are provided in Section [5.1](#).

Patients will be monitored for acute hypersensitivity reactions for at least 1 hour after the end of the injection. Epinephrine and parenteral diphenhydramine must be readily available for immediate use if required to treat a hypersensitivity reaction; site personnel must be able to detect and treat such reactions.

Guidelines for etrolizumab administration will be provided in supporting documents.

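### The Figure 1 note gives one injection volume, 0.01 mL/kg, for both regimens; at 150 mg/mL that is half the stated 3 mg/kg Q8W dose and conflicts with the Synopsis and Section 4.3

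*Combined protocol and SAP*

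**What the plan says.** Section 3.1 defines the two arms by dose and interval: "The high-frequency dose of 1.5 mg/kg etrolizumab will be administered Q4W (Weeks 0, 4, 8, and 12", and "The low-frequency dose of 3.0 mg/kg etrolizumab will be administered Q8W (Weeks 0 and 8".

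The full line in the Figure 1 note, also in Section 3.1, is "Etrolizumab dose: 1.5 mg/kg Q4W or 3 mg/kg Q8W SC injection of 0.01 mL per kg of patient weight". It names two regimens and one volume. Its second half, "3 mg/kg Q8W SC injection of 0.01 mL per kg of patient weight", sets that volume next to the Q8W regimen.

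Section 4.3 gives a volume for each regimen: "one subcutaneous injection of 0.01 mL per kg of patient weight (1.5 mg/kg) Q4W", and "injection of 0.02 mL per kg of patient weight (3 mg/kg) Q8W". The Synopsis, under Investigational Medicinal Products, gives the same two pairs.

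Section 4.3.1.1 gives the strength: "The drug product contains 150 mg/mL of etrolizumab".

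Section 4.3.2.1, on administration, refers to Section 3.1 for a summary of the regimens. It restates the mg/kg doses (Q4W first, then Q8W) and lists the volumes as 0.01 or 0.02 mL/kg, given "at each treatment visit based on the treatment regimen (the low or high frequency arm").

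**The concern.** A volume per kilogram and a concentration together fix the dose. The note offers one volume for two doses that differ by a factor of 2, so it cannot fit both. Whether the 0.01 mL/kg is read as belonging to both regimens or only to the Q8W regimen printed next to it, it does not give 3 mg/kg.

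Dose and interval are the experimental factor in this study. The primary endpoints (Table 1) are Cmax, AUCtau, half-life, trough concentration and β7 receptor occupancy, all of which depend on the amount injected. Section 3.3.2 says that two doses were chosen so that dose proportionality can be evaluated in children. The numbers are small: Section 3.1 plans about 24 patients, to yield at least 12 with evaluable PK profiles, and Section 9.4 spreads them over about 20 sites. Most sites would therefore dose one or two patients, and a volume error in even one Q8W patient would matter.

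**Working it through.** **Inputs.** Strength 150 mg/mL (Section 4.3.1.1). Doses and schedules: 1.5 mg/kg at Weeks 0, 4, 8 and 12, and 3.0 mg/kg at Weeks 0 and 8 (Section 3.1). Volumes: 0.01 mL/kg for Q4W and 0.02 mL/kg for Q8W (Synopsis, Section 4.3); 0.01 mL/kg only (Figure 1 note).

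**Formula.** Dose (mg/kg) = volume (mL/kg) × 150 mg/mL. Cumulative dose over the 16-week treatment period = dose per visit × number of dosing visits (4 for Q4W, 2 for Q8W).

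**Step 1: reproduce the Section 4.3 pairs.**
- Q4W: 0.01 × 150 = 1.5 mg/kg, as stated.
- Q8W: 0.02 × 150 = 3.0 mg/kg, as stated.

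**Step 2: apply the Figure 1 note.**
- Q4W: 0.01 × 150 = 1.5 mg/kg, which agrees with the stated dose.
- Q8W: 0.01 × 150 = 1.5 mg/kg against a stated 3 mg/kg; 1.5 / 3 = 0.5.

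**Step 3: cumulative dose.**

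| Source of the volume | Q4W, 4 visits | Q8W, 2 visits |
|---|---|---|
| Synopsis and Section 4.3 | 4 × 1.5 = 6 mg/kg | 2 × 3.0 = 6 mg/kg |
| Figure 1 note, single volume for both | 4 × 1.5 = 6 mg/kg | 2 × 1.5 = 3 mg/kg |

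Under the Synopsis and Section 4.3 the arms have equal totals and a 2:1 ratio of dose per injection. Under the note the dose per injection is the same in both arms and the Q8W total is half the Q4W total. The arms would then differ only in interval and in number of injections.

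**Step 4: size in one patient.** At 13 kg, the minimum weight for entry, a Q8W injection is 0.26 mL (39 mg) by Section 4.3 and 0.13 mL (19.5 mg) by the note. At 40 kg, the stratification cut-point, it is 0.80 mL (120 mg) against 0.40 mL (60 mg).

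**Step 5: where a reader would meet the note.** Section 4.3.2.1 defers to Section 3.1 for the regimens. In the text of Section 3.1, the Figure 1 note is the only place that states a volume. The drawing itself is not available here; the check rests on the printed note alone.

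**The case against.** The strongest reply is that this is one incomplete line under a schema. The dose in mg/kg for each interval is the same in the Synopsis, Sections 3.1, 3.3.2, 4.3 and 4.3.2.1, the last footnote to Appendix 1a, and the Figure 1 note itself. Both places that explicitly pair a volume with a dose and an interval agree with each other and reproduce at 150 mg/mL. The note may simply have lost a second volume. Section 4.3.2.1 also says that administration guidelines will come in supporting documents, and Section 5.4.4 mentions a pharmacy manual; neither can be seen here.

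Much of this stands. It makes an actual dosing error less likely, and it means that no misdosing can be claimed. It does not remove the contradiction. An omitted second volume leaves the same mismatch on the page, and supporting documents that cannot be seen cannot be assumed to correct it.

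A reader might go further and infer that Section 4.3.2.1 reverses the volumes. It lists 0.01 and then 0.02 mL/kg but names the low-frequency arm before the high-frequency arm. Matched in order, that would give Q8W 1.5 mg/kg and Q4W 0.02 × 150 = 3 mg/kg, with totals of 2 × 1.5 = 3 and 4 × 3 = 12 mg/kg: a doubled Q4W dose and a 4-fold gap between arms. The text does not support this. The sentence does not say that the two lists correspond item by item, and the volumes follow the order of the regimens given earlier in the same paragraph, Q4W and then Q8W. The words in parentheses explain what is meant by the treatment regimen; they do not assign volumes to arms. The order is loose and could be clearer, but it is an ambiguity and not a wrong assignment.

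**Conclusion.** The point holds for the Figure 1 note. At the stated strength, its single volume delivers half the stated Q8W dose, 1.5 instead of 3 mg/kg per injection and 3 instead of 6 mg/kg in total, and it contradicts the Synopsis and Section 4.3. The discrepancy affects Q8W only and runs downward; the documents do not support a doubled dose in either arm.

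The result rests on two things: the 150 mg/mL strength applies to the vials used in this study, and the note reads as printed. If a site used the note's volume for Q8W, Cmax in that patient would be roughly half the intended value, on the assumption that the approximate dose proportionality reported in adults (Section 1.3) carries over to children. Nothing in the documents shows that this has happened. The point deserves correction because it concerns an injection volume, in the section to which the administration instructions refer, in what Section 1.4 calls the first pediatric study of the drug.

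**What to change.** Reconcile four places: the Synopsis (Investigational Medicinal Products), the Figure 1 note, Section 4.3 and Section 4.3.2.1. In each, name each arm with its mg/kg, mL/kg and interval, and check each volume against 150 mg/mL. In Section 4.3.2.1, attach each volume to a named arm in place of the closing parenthesis. Confirm that the pharmacy manual and the administration guidelines agree. If Q8W patients have already been dosed, compare their dosing records with the assigned dose before the PK analysis. It is for the sponsor to settle the dose and volume; no view is taken here on which is right.

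The cost is a wording change in the note, a clarification in Section 4.3.2.1 and a check of the supporting documents. No design element, sample size or analysis changes.

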**Figure 2 Study Schema: Open-label Extension Phase**

**Figure 3 Study Schema: Progressive Multifocal Leukoencephalopathy Monitoring Phase**

OLE = open-label extension; PML = progressive multifocal leukoencephalopathy.

### **3.1.1 Safety Monitoring Committee**

The Sponsor's Safety Monitoring Committee will assess safety on an ongoing basis. The Committee's evaluations will include, but are not limited to, adverse events, serious adverse events, and laboratory abnormalities. This committee will include a medical monitor, drug safety scientist, and biostatistician from the Sponsor. The Safety Monitoring Committee may request that additional Sponsor scientists (e.g., PK or clinical scientists) participate in data analysis.

### **3.3 RATIONALE FOR STUDY DESIGN**

#### **3.3.1 Rationale for Patient Population**

Etrolizumab will be studied in children between 4 and 11 years of age and adolescents from 12 to <18 years of age. Children younger than 4 years of age will not be studied on the grounds that studies would be impossible or highly impractical due to the small number of patients in this age group and because the specific medicinal product has the potential to be unsafe in this age range of the pediatric population.

In the United States, the incidence of UC in children younger than 4 years of age is very low, with the annual incidence in this age group ranging between 0.2–0.7 per 100,000 and prevalence ranging between 1.1–2.3 per 100,000 (Herrinton et al. 2008; Abramson et al. 2010; Malaty et al. 2010). Similarly, the incidence of CD in the United States in children younger than 4 years of age is very low and presentation rarely occurs before 4 years of age (de Greef et al. 2013). Because of the small number of patients with UC and CD in children 0–4 years of age, it is impossible or highly impracticable to conduct a study in this age population. In children approximately  $\geq$ 6 years of age, the functional development of the immune system and the GI tract is similar to that of adults (Holladay and Smialowicz 2000).

The nonclinical safety strategy supporting etrolizumab clinical development in children 4–17 years of age takes into consideration the age of animals in the repeat-dose toxicity studies, as well as the planned assessment of the F1 generation in the proposed prenatal/postnatal developmental study. The male animals included in the 12– and 26-week repeat-dose toxicity studies in cynomolgus monkeys were 2–4.2 years of age at study initiation (comparable to approximately 8–17 years of age in humans, with a conversion factor of 4) and were sexually immature or peripubertal as assessed by microscopic evaluation of relevant reproductive tract tissues at the end of dosing in both studies.

The female animals in the 12-week study were 2.3–3.3 years of age at study initiation (comparable to approximately 9–13 years of age in humans). Although the definitive maturity for females was not specifically captured in the microscopic evaluation of reproductive tissues in this study, the animals were likely peripubertal based on their age range. The female animals in the 26-week study were of 3.2–4.2 years of age at study initiation (comparable to approximately 13–17 years of age in humans) and did demonstrate sexual maturity at the end of the 6-month dosing phase as assessed by microscopic evaluation of relevant reproductive tract tissues.

No findings attributed to etrolizumab were identified in male and female reproductive tissues in these studies, as assessed by organ weights and macroscopic and microscopic evaluation. In the 26-week toxicity study in mice, animals were 6–7 weeks of age at study initiation and should have reached puberty before the end of study (Beckman and Feuston 2003; Marty et al. 2003). No drug-related effects were found in male or female reproductive tissues following etrolizumab administration, as assessed by organ weights and macroscopic and microscopic evaluation.

The pharmacokinetics of monoclonal antibodies in pediatric patients could be different from adults due to the difference in catabolic enzymes, changes in body composition, elimination in organs, receptor-mediated endocytosis and target receptor expression. Etrolizumab was cleared partially through the target-mediated drug disposition.

The target receptor expression in pediatrics may be different from adults. The differences lead to changes in the volume of distribution, clearance, and

absorption of monoclonal antibody. Due to the complexity of the contributors involved, the direction and extent of the differences in pediatric population are not always readily predictable. The results obtained from this Phase I PK/PD study in pediatrics will provide a solid rationale for a proper dosing adjustment for pediatric population.

### **3.3.2 Rationale for Etrolizumab Dose and Schedule**

Two dosing regimens are selected in this pediatric PK/PD study. One is 1.5 mg/kg every 4 weeks, dosed on Week 0, 4, 8, and 12, the other is 3 mg/kg every 8 weeks, dosed on Weeks 0 and 8. The rationale of the dose selection for this pediatric study is to allow evaluation of full PK and PD profiles in a pediatric population and to understand the kinetics at both linear and nonlinear concentration ranges. Two doses will allow the dose proportionality to be evaluated in a pediatric population and longer dosing interval helps to evaluate PK and PD profiles within the nonlinear concentration range.

The PK and PD ( $\beta 7$  receptor occupancy [RO]) profiles following SC administration of 1.5 mg/kg Q4W and 3 mg/kg Q8W were simulated by extrapolating from an adult population PK (PopPK)/PD model. The simulated median RO profile suggested that RO was fully saturated within the dosing interval across all age groups following 1.5 mg/kg Q4W. The median RO following 3 mg/kg Q8W was fully saturated most of time within the dosing interval for patients with body weight higher than 70 kg. For patients with a body weight  $<30$  kg, the duration of maximum RO was about half of the dosing interval.

The simulated median  $C_{max}$  and  $AUC_{\tau}$  from patients with a body weight of 100 kg were 21.4  $\mu$ g /mL and 534  $\mu$ g • day/mL following 3 mg/kg Q8W. The safety of these proposed dosing regimens in pediatric population is well supported by nonclinical safety data. At the no-observed-adverse-effect-level (NOAEL) dose of 50 mg/kg SC  $\times$  27 doses in cynomolgus monkey given every week for 26 weeks (the highest dose tested), the steady-state  $C_{max}$  and  $AUC_{183-190}$  were 1250  $\mu$ g/mL and 9310  $\mu$ g • day/mL, respectively. On the basis of the steady state  $C_{max}$  or systemic exposure (AUC), the NOAEL dose in cynomolgus monkeys provides safety factors of 58- or 17-fold, respectively, for the highest proposed dose of 3 mg/kg Q8W. Compared to the highest dose tested in humans (an LD of 420 mg SC at Week 1, and 300 mg SC at Weeks 2, 4, and 8), the safety margins for the dose of 3 mg/kg Q8W are approximately 2-fold for both  $C_{max}$  and  $AUC_{\tau}$ .

### **3.3.3 Rationale for PK Sampling Schedule**

The sampling schedule that follows the first and last dose of etrolizumab is designed to provide sufficient data to define the critical PK and PD parameters and to understand the absorption, distribution, and elimination of this drug in a pediatric IBD population, including time to maximum observed concentration ( $t_{max}$ ), clearance, and elimination half-life ( $t_{1/2}$ ).

Considering blood draw restrictions in the pediatric population, optimized blood sampling was planned to allow determination of etrolizumab PK parameters such as  $AUC_{\tau}$  (following the last dose),  $C_{max}$  (following the first and last doses), steady-state concentration at the end of a dosing interval (i.e., just prior to next drug administration) ( $C_{trough}$ ) and half-life ( $t_{1/2}$ ) with minimal number of samples necessary.  $C_{max}$  estimates will be based on a single time point after the first and last dose where the maximum concentrations are expected based on the adult PK data. PK time points have been aligned with the proposal for the European Medicines Agency (EMA) health authority.

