The pharmacokinetics and pharmacodynamics of etrolizumab were characterized in Phase I (ABS4262g) and Phase II (ABS4986g) studies in adult patients with moderately to severely active UC. Study ABS4262g tested both single dose and multiple doses of etrolizumab either IV or subcutaneous (SC) at dose levels of 0.3–10 mg/kg (single dose IV), 3 mg/kg (single dose SC), 0.5–3 mg/kg SC or 4 mg/kg IV (multiple doses given once every 4 weeks [Q4W]  $\times$  3). Study (ABS4986g) tested two dose regimens: 100 mg (nominal dose) SC Q4W and 420 mg SC at Week 1 followed by 300 mg SC at Weeks 2, 4, and 8. The pharmacokinetic (PK) profile of etrolizumab is generally dose proportional with regard to maximum serum concentration observed ( $C_{max}$ ) and area under the serum concentration-time curve from time zero to infinity ( $AUC_{inf}$ ) (or AUC within the last dose interval [ $AUC_{\tau}$ ]) for the dose ranges tested. The mean elimination half-life in UC patients was approximately 13–15 days following multiple doses of 100 mg and 300 mg SC administration.

In study ABS4262g, a dose-dependent increase in the duration of  $\beta 7$  receptor occupancy was observed following a single IV dose of 0.3, 1 and 10 mg/kg of etrolizumab. The group mean occupancy was maintained for approximately 2 weeks, 6 weeks, and 10 weeks, respectively. In study ABS4986g, maximal/near maximal  $\beta 7$  receptor occupancy was observed up to 71 days following multiple doses of 100 mg and 300 mg SC administration.

Exploratory PK/pharmacodynamics (PD) analysis showed a relationship between PK (serum drug levels) and PD ( $\beta 7$  receptor occupancy) in which approximately 1–3  $\mu$ g/mL of serum etrolizumab maintained maximal/near maximal occupancy of  $\beta 7$  integrin on peripheral blood mucosal-homing T cell subsets.

The safety of etrolizumab *has been assessed in Phase I, Phase II, and five Phase III studies in adult patients with moderate to severe UC.*

The following is a summary of the etrolizumab safety experience to date:

- No significant adverse safety signal, including any evidence of increased rates of serious or opportunistic infections, was associated with etrolizumab treatment in the Phase I or Phase II trials in adult patients with moderately to severely active UC who received either single or multiple doses of IV or SC etrolizumab.

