**Appendix 1a**  
**Schedule of Assessments: Randomized Treatment Phase (Treatment Period)**

Assessments	Screening Day b –35 to –0	Study Days (±3 days) a											Early Withdrawal from Treatment or Discontinuation
		1 c	4	28 (Wk 4)	56 (Wk 8)	60 d	70 d	84 (Wk 12)	88	98	112 (Wk 16)	Unscheduled Visit e	
Informed consent	x												
Review eligibility criteria	x	x f											
Demographic data	x												
Pregnancy test g	x	x f		x f	x f			x f			x		x
Vital signs (BP and pulse)	x	x f	x	x f	x f			x f	x	x	x	x	x
ECG	x												x
Chest X-ray h	x												
Height	x	x		x	x			x			x	x	x
Weight	x	x		x	x			x			x	x	x
Tanner Stage	x												x
Medical history	x												
Physical examination i	x							x		x		x	x
PML neurologic examination j	x		x					x				x e	x
Hematology	x	x f		x	x f			x		x	x	x e	x l
ESR k	x			x	x			x			x	x	x
Chemistry	x	x f		x k	x f			x k		x	x	x e	x l
Urinalysis	x	x f			x f							x e	

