## Appendix 1a

### Schedule of Activities: Randomized Treatment Phase (Treatment Period) (cont.)

Assessments	Screening Day b – 35 to – 0	Study Days ( $\pm 3$ days) a												Early Withdrawal from Treatment or Discontinuation
		1 c	4	28 (Wk 4)	56 (Wk 8)	60 d	70 d	84 (Wk 12)	88	98	112 (Wk 16)	Unscheduled Visit e		
Concomitant medications		x	x	x	x			x	x	x	x	x	x	x
Adverse events	x	x	x	x	x			x	x	x	x	x	x	x
Randomization		x w												
Etrolizumab administration Q4W a, x		x		x	x			x						
Etrolizumab administration Q8W a, x		x			x									

ADA=anti-drug antibody; BP=blood pressure; CD=Crohn's Disease; CMV=cytomegalovirus; CRP=C-reactive protein; ECG=electrocardiogram; eCRF=electronic Case Report Form; ESR=erythrocyte sedimentation rate; HBc=HBV core antibody total; HBsAg=HBV surface antigen; HBV=hepatitis B virus; HCV=hepatitis C virus; JCV=John Cunningham virus; MAdCAM-1=mucosal vascular addressin cell adhesion molecule-1; MCS=Mayo Clinic Score; PD=pharmacodynamics; PK=pharmacokinetic; PML=progressive multifocal leukoencephalopathy; PCDAI=Pediatric Crohn's Disease Activity Index; PUCAI=Pediatric Ulcerative Colitis Activity Index; Q4W=every 4 weeks; Q8W=every 8 weeks; TB=tuberculosis; UC=Ulcerative Colitis; Wk=week.

Note: All study assessments and blood draws are to be conducted prior to study drug administration.

a The time window for days etrolizumab is administered is  $\pm 1$  day.

b All assessments must be performed after obtaining informed consent.

c Day 1 of Week 0.

d These samples are only collected for patients receiving 3 mg/kg etrolizumab administration Q8W.

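### The single near-peak sample behind each primary Cmax has a ±3-day window not counted from the actual dose, so a draw 1 day after dosing is within protocol

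*Combined protocol and SAP*

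**What the plan says.** Table 1 lists Cmax among the PK parameters of the primary objective and defines it in the table note as the highest observed concentration. Section 3.3.3, citing limits on paediatric blood draws, says that Cmax "estimates will be based on a single time point after the first and last dose", chosen "where the maximum concentrations are expected based on the adult PK data". It gives no adult Tmax.

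In Appendix 1a the near-peak draws are Day 4 after the first dose, Day 60 after the last Q8W dose (Day 56) and Day 88 after the last Q4W dose (Day 84). Footnote d says of Days 60 and 70: "These samples are only collected for patients receiving 3 mg/kg etrolizumab administration Q8W". All of these visits stand under a column header that begins "Study Days (±3 days". Footnote a is narrower but covers dosing days only: "The time window for days etrolizumab is administered is" ±1 day. The table note adds: "All study assessments and blood draws are to be conducted prior to study drug administration".

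The first-dose day is given in two ways. Footnote c makes it Day 1 of Week 0, while footnote w refers to a first dose at Day 0.

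Section 6.4 derives Cmax and Tmax after the first and final dose by non-compartmental analysis. It lists and summarises them with means, ranges, standard deviations and coefficients of variation. It does not say whether actual sampling times are used or how an off-schedule draw is handled.

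**The concern.** One sample stands for the peak only if it is taken near the peak. The nominal interval from dose to draw is 3 or 4 days and the window is ±3 days, so the permitted early error is about as large as the interval itself. Nothing in the protocol sets an earliest draw or counts the draw from the dose actually given. Section 4.5 does count the safety follow-up visits from the last dose, so the idea is available but is not applied here.

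A sample taken while the drug is still being absorbed would be listed as that child's Cmax. After the first dose, no later sample could correct it, because the next draw is Day 28. Section 3.3.2 also wants the two regimens to inform dose proportionality, and unequal timing of the last-dose draws could disturb that comparison.

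**Working it through.** **1. Permitted interval from dose to draw (Appendix 1a)**

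- First dose, Day 1 reading: Day 4 ± 3 minus Day 1 = 0–6 days. The 0-day case is effectively excluded, because blood on dosing days is drawn before dosing. That leaves 1–6 days.
- First dose, Day 0 reading: Day 4 ± 3 minus Day 0 = 1–7 days.
- Last dose on its nominal day: 60 ± 3 − 56 and 88 ± 3 − 84 both give 1–7 days.
- Last dose given one day early: 63 − 55 = 8 and 91 − 83 = 8 days at the latest.

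A 1-day draw is compliant for both doses, in both arms, on either reading of the first-dose day.

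**2. What a draw reads as a share of the true peak**

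The plan gives no figure for this, so a model is assumed: one compartment, first-order SC absorption, linear clearance.

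C(t) ∝ Σ [exp(−ke·(t + iτ)) − exp(−ka·(t + iτ))], summed over 1 dose (first), 2 doses with τ = 56 days (last Q8W) or 4 doses with τ = 28 days (last Q4W).

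- ke = ln 2 / half-life. Section 1.3: "The mean elimination half-life in UC patients was approximately" 13–15 days.
- ka is solved from ln(ka/ke)/(ka − ke) = first-dose Tmax. Tmax is assumed to be 3–7 days, which gives ka of 0.30–1.10 per day.

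Example (half-life 13 days, Tmax 4 days): ke = 0.0533, ka = 0.695. At 1 day: 0.948 − 0.499 = 0.449. At the 4-day peak: 0.808 − 0.062 = 0.746. Ratio: 0.449/0.746 = 0.60.

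| Days after dose | First dose | Last Q8W | Last Q4W |
|---|---|---|---|
| 1 | 37–75% | 42–77% | 62–84% |
| 2 | 62–96% | 66–97% | 79–98% |
| 3 | 79–100% | 81–100% | 90–100% |
| 4 | 90–100% | 91–100% | 96–100% |
| 7 | 85–100% | 85–100% | 84–99% |
| 8 | not permitted | 80–99% | 80–97% |

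If the peak is at 3–4 days, as the placement of the draws suggests, a 1-day draw reads 60–75%, 63–77% and 74–84%. The corresponding 2-day figures are 87–96%, 88–97% and 93–98%.

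**3. Check against the plan's own exposure figures**

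Section 3.3.2 gives simulated medians at 100 kg on 3 mg/kg Q8W: AUCτ 534 µg·day/mL and Cmax 21.4 µg/mL. The ratio is 534/21.4 = 24.95 days. The assumed model range gives 20.8–27.3 days, which brackets it. Solving ka to match 24.95 implies a first-dose Tmax of 4.9–6.5 days and 1-day readings of 39–52% (first), 45–57% (last Q8W) and 63–71% (last Q4W).

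**4. If Cmax is the highest observed value**

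A further sample falls 14 days after the last dose (Day 70 for Q8W, Day 98 for Q4W). It reads 58–82% (Q8W) or 58–79% (Q4W) of the peak. Taking the higher of the 1-day and 14-day values gives 63–82% (Q8W) and 68–84% (Q4W).

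**5. Effect on an arm mean**

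With one 1-day draw and the others at 4 days, under the single-time-point definition, the mean is multiplied by [(n − 1)·f4 + f1]/(n·f4), where f1 and f4 are the shares of the peak at 1 and 4 days. For Q8W at the slow-absorption end with n = 12: (11 × 0.911 + 0.425)/(12 × 0.911) = 0.956. Over the full range the factor is 0.956–0.982 (Q8W) and 0.971–0.989 (Q4W), so the mean falls by about 2–4% and 1–3%. If only the minimum of 12 evaluable patients were reached, split 6 and 6, the falls would be about 4–9% and 2–6%.

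**The case against.** - **The laboratory manual may already be tighter.** Section 4.5.6 sends sampling procedures there, and it is not among these documents. This stands. A reader might infer that nothing controls the draw time, and the documents do not support that. They show only that the protocol does not.
- **Later samples limit the last-dose error.** Under Table 1's definition the 14-day sample counts, and the floor for Q8W rises from 42% to about 63%. This stands, so 42% should not be quoted as the last-dose worst case without naming the definition. Section 3.3.3 points to the single time point, and the two passages need reconciling. After the first dose the 14-day argument gives no help.
- **The peak time is unknown.** No absorption rate is given, and Section 3.3.1 says "Etrolizumab was cleared partially through the target-mediated drug disposition", so a linear model is approximate. This stands for the exact percentages. The direction holds for any Tmax of about 3 days or more; with a Tmax near 2 days, a 1-day draw would read about 90%.
- **The consequence is small.** PK is summarised descriptively with no powered comparison, and nothing suggests that sites would habitually use the early edge. This stands for arm means. A reader might infer that the dose-proportionality assessment is invalid, but the last-dose shift from one early draw is a few per cent, and both arms share the Day 4 visit after the first dose.
- **A same-day post-dose draw.** The day arithmetic alone might suggest that one is allowed. The pre-dose sampling rule effectively excludes it.
- **Time points are aligned with the EMA proposal.** Section 3.3.3 says this of time points and does not mention windows.

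**Conclusion.** The point holds as a protocol gap worth closing; it is not a flaw that undermines the study. That a 1-day draw is compliant is exact arithmetic from Appendix 1a. That it would read well below the peak depends on the assumed model: 37–75% after the first dose, and after the last dose 42–77% (Q8W) or 62–84% (Q4W) on the single-time-point definition, or 63–82% and 68–84% on the highest-observed definition. Even at the favourable Tmax of 3–4 days, 16–40% of the peak is missed. The late edge matters less: a 7-day draw still reads 84% or more.

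The damage falls on individual listed values, ranges and CVs. Arm means move little unless several draws are early. Confidence is medium, because the adult Tmax and the laboratory manual are not available here.

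**What to change.** In Appendix 1a:

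1. Reconcile footnotes c and w on whether the first dose is Day 1 or Day 0, since the nominal interval to the Day 4 draw is 3 days on one reading and 4 on the other.
2. Count the Day 4, 60 and 88 PK draws from the actual preceding dose, and replace ±3 days with a narrower window around the nominal interval. Set the limits from the sponsor's adult Tmax data, for example nominal ±1 day, or ±2 days if those data support it. At ±1 day, last-dose draws (3–5 days) would read 81–100% (Q8W) and 90–100% (Q4W) on the assumptions above. At ±2 days around a 3-day first-dose interval, a 1-day draw would still be allowed (3 − 2 = 1), so the lower limit needs checking against the reading adopted in item 1. A fixed 3-day lower limit is not clearly better: if the peak is at 3–4 days it would bar a 2-day last-dose draw reading 88–98%, while a 7-day upper limit would admit one reading 84–92%. If the laboratory manual already has a limit, copy it in.
3. Keep draws outside the window, flagged with their actual times, so that no patient is lost from the evaluable set.

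In Section 6.4, state that actual sampling times are used, and adopt one Cmax definition that reconciles Section 3.3.3 with Table 1.

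The cost is a footnote and a sentence, slightly tighter booking of two visits per patient, and a few more recorded deviations. No blood sample or visit is added.
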